## 7.4 HANDLING OF MISSING DATA

[Table 7.4: 1](#) describes how patients will be classified for the analysis of PFS.

**Proprietary confidential information.**

© 2016 Boehringer Ingelheim International GmbH or one or more of its affiliated companies. All rights reserved.

This document may not - in full or in part - be passed on, reproduced, published or otherwise used without prior written permission.

Table 7.4: 1 Rules to determine events and censoring for PFS

Rule #	Situation	Outcome (event or censored)	Date of PFS event or censoring
1	No baseline tumour assessment (no death before second scheduled assessment)	censored	Date of randomisation
2	Progressed from central imaging (no missed radiologic assessments)	event	Date of PD
3a	Non-PD from central imaging  , death before next scheduled assessment	event	Date of death
3b	Non-PD from central imaging  , one missed assessment, death or progression after date of missed assessment, but before a second scheduled assessment	event	Date of PD or death
3c	Non-PD from central imaging  , more than one consecutive missed assessment, death or progression after date of second missed assessment	censored	Date of last imaging before missed assessment
3d	Non-PD from central imaging  , more than one consecutive missed assessment, non-PD according to imaging after missed assessments	censored	Date of last non-PD imaging
4	New anti-cancer medication before progression or death	censored	Date of last imaging before new anti-cancer medication
5	Death before the scheduled date of first imaging	event	Date of death
6a	No imaging performed post-baseline, patient dies between first and second scheduled assessments	event	Date of death
6b	No imaging performed post-baseline, patient dies after second scheduled assessment	censored	Date of randomisation
6c	No imaging performed post-baseline, vital status is unknown or patient known to be alive	censored	Date of randomisation
7	Alive and not progressed from central imaging (no missed assessments)	censored	Date of last imaging

 - From the last assessment at which CR, PR or SD was assessed.

## 7.5 RANDOMISATION

Equal proportions of patients will be randomised to afatinib and to erlotinib. Randomization will be performed in blocks and stratified by race (Eastern Asian vs. non-Eastern Asian). The process of randomisation will be performed as described in [Section 4.1.2](#).

## 7.6 DETERMINATION OF SAMPLE SIZE

[Table 7.6: 1](#) shows the number of PFS events required for the primary analysis. The Table indicates that 372 PFS events would be expected to provide 90% power for the log-rank test,

Proprietary confidential information.

© 2016 Boehringer Ingelheim International GmbH or one or more of its affiliated companies. All rights reserved.

This document may not - in full or in part - be passed on, reproduced, published or otherwise used without prior written permission.

presuming a hazard ratio of 0.714 for afatinib relative to erlotinib (corresponding to median PFS times of 14 vs. 10 weeks, respectively). Data on file ([R10-6208](#)).

Table 7.6: 1 Number of PFS events required for 80% and 90% power

	80% Power	90% Power
Median PFS for afatinib	14 weeks	14 weeks
Median PFS for erlotinib	10 weeks	10 weeks
Hazard ratio of afatinib vs erlotinib	0.714	0.714
Number of events required for both groups 	278	372
Total Number of randomised patients	350	500

 log-rank test, alpha = 0.05, two-sided

 The number of required events was calculated using EAST-5 software excluding interim analysis, with patients randomised in a 1:1 ratio at a rate of 6 patients per week.

Table 7.6: 2 indicates that 632 deaths would be expected to provide 80% power for the log-rank test, presuming a hazard ratio of 0.800 for afatinib relative to erlotinib (corresponding to median survival times of 8.75 vs. 7.00 months, respectively).

Table 7.6: 2 Number of deaths required for 80% and 90% power

	80% Power	90% Power
Median OS for afatinib	8.75 months	8.75 months
Median OS for erlotinib	7.00 months	7.00 months
Hazard ratio of afatinib vs erlotinib	0.80	0.80
Number of events required for both groups 	632	845
Total Number of randomised patients	800	1040

 log-rank test, alpha = 0.05, two-sided

 The number of required events was calculated using EAST-5 software excluding interim analysis, with patients randomised in a 1:1 ratio at a rate of 36 patients per month.

## **8. INFORMED CONSENT, DATA PROTECTION, TRIAL RECORDS**

The trial will be carried out in compliance with the protocol, the principles laid down in the Declaration of Helsinki, in accordance with the ICH Harmonised Tripartite Guideline for Good Clinical Practice (GCP) and relevant BI Standard Operating Procedures (SOPs). Standard medical care (prophylactic, diagnostic and therapeutic procedures) remains in the responsibility of the treating physician of the patient.

The investigator should inform the sponsor immediately of any urgent safety measures taken to protect the study subjects against any immediate hazard, and also of any serious breaches of the protocol/ICH GCP.

The rights of the investigator and of the sponsor with regard to publication of the results of this trial are described in the investigator contract. As a general rule, no trial results should be published prior to finalisation of the Clinical Trial Report.

### **8.1 STUDY APPROVAL, PATIENT INFORMATION, AND INFORMED CONSENT**

This trial will be initiated only after all required legal documentation has been reviewed and approved by the respective Institutional Review Board (IRB) / Independent Ethics Committee (IEC) and competent authority (CA) according to national and international regulations. The same applies for the implementation of changes introduced by amendments.

Prior to patient participation in the trial, written informed consent must be obtained from each patient (or the patient's legally accepted representative) according to ICH GCP and to the regulatory and legal requirements of the participating country. Each signature must be personally dated by each signatory and the informed consent and any additional patient-information form retained by the investigator as part of the trial records. A signed copy of the informed consent and any additional patient information must be given to each patient or the patient's legally accepted representative.

The patient must be informed that his/her personal trial-related data will be used by Boehringer Ingelheim in accordance with the local data protection law. The level of disclosure must also be explained to the patient.

The patient must be informed that his / her medical records may be examined by authorised monitors (CML/CRA) or Clinical Quality Assurance auditors appointed by Boehringer Ingelheim, by appropriate *IRB / IEC* members, and by inspectors from regulatory authorities.

## 8.2 DATA QUALITY ASSURANCE

A quality assurance audit/inspection of this trial may be conducted by the sponsor or sponsor's designees or by IRBs/IECs or by regulatory authorities. The quality assurance auditor will have access to all medical records, the investigator's trial-related files and correspondence, and the informed consent documentation of this clinical trial.

## 8.3 RECORDS

Case Report Forms (CRFs) for individual patients will be provided by the sponsor, either on paper or via remote data capture. For drug accountability, refer to [Section 4.1.8](#).

### 8.3.1 Source documents

Source documents provide evidence for the existence of the patient and substantiate the integrity of the data collected. Source documents are filed at the investigator's site.

Data entered in the eCRFs that are transcribed from source documents must be consistent with the source documents or the discrepancies must be explained. The investigator may need to request previous medical records or transfer records, depending on the trial; also current medical records must be available.

For eCRFs all data must be derived from source documents.

### 8.3.2 Direct access to source data and documents

The investigator / institution will permit trial-related monitoring, audits, IRB / IEC review and regulatory inspection, providing direct access to all related source data / documents. CRFs/eCRFs and all source documents, including progress notes and copies of laboratory and medical test results must be available at all times for review by the sponsor's clinical trial monitor, auditor and inspection by health authorities (e.g. FDA). The Clinical Research Associate (CRA) / on site monitor and auditor may review all CRFs/eCRFs, and written informed consents. The accuracy of the data will be verified by reviewing the documents described in [Section 8.3.1](#).

## 8.4 LISTEDNESS AND EXPEDITED REPORTING OF ADVERSE EVENTS

### 8.4.1 Listedness

To fulfil the regulatory requirements for expedited safety reporting, the sponsor evaluates whether a particular adverse event is "listed", i.e. is a known side effect of the drug or not. Therefore a unique reference document for the evaluation of listedness needs to be provided. For afatinib, this is the current version of the Investigator's Brochure ([U03-3218](#)). For erlotinib this is the EU SPC. The current versions of these reference documents are to be provided in the ISF. No AEs are classified as listed for study design or invasive procedures.

#### **8.4.2 Expedited reporting to health authorities and IECs/IRBs**

Expedited reporting of serious adverse events, e.g. suspected unexpected serious adverse reactions (SUSARs) to health authorities and IECs/IRBs, will be done according to local regulatory requirements. Further details regarding this reporting procedure are provided in the ISF.

#### **8.5 STATEMENT OF CONFIDENTIALITY**

Individual patient medical information obtained as a result of this trial is considered confidential and disclosure to third parties is prohibited with the exceptions noted below. Patient confidentiality will be ensured by using patient identification code numbers.

Treatment data may be given to the patient's personal physician or to other appropriate medical personnel responsible for the patient's welfare. Data generated as a result of the trial need to be available for inspection on request by the participating physicians, the sponsor's representatives, by the IRB / IEC and the regulatory authorities.

#### **8.6 COMPLETION OF TRIAL**

The EC/competent authority in each participating EU member state needs to be notified about the end of the trial (last patient/patient out, unless specified differently in [Section 6.2.3](#) of the CTP) or early termination of the trial.

## 10. APPENDICES

### 10.1 RECIST 1.1 CRITERIA

The criteria below are based on RECIST 1.1 ([R09-0262](#)).

The preferred method of assessment is a spiral CT scan with IV and oral contrast, unless IV and/or oral contrast are medically contraindicated. CT scans of the chest, abdomen and other areas of known or newly suspected disease must be performed. Scans of the abdomen, pelvis and other areas of the body, but not chest, may be done with MRI instead of CT.

Skin lesions followed as target lesions must be documented by colour digital photography and must include in the image a ruler with millimetre subdivisions and a label that includes the patients ID and date.

Bone scans (using m-technetium polyphosphonate scintigraphy) are recommended at baseline if the patient has any signs and symptoms consistent with bone metastasis or a history of bone metastasis. Bone metastasis identified at baseline must be documented and assessed according to RECIST 1.1 at the times of the other tumour measurements indicated in the [flow chart](#). During the study bone scans should be repeated as clinically indicated in patients without bone metastasis at Baseline.

For the purposes of this study, patients should be re-evaluated for response at weeks 8, 12, 16, and every 8 weeks thereafter. In the event of a treatment delay, interruption or discontinuation of treatment, tumour assessment should continue to follow the original schedule.

After approval of protocol version 3, tumour assessment will be performed every 18 weeks unless clinically indicated until progression or start of further treatment.

Follow-up tumour assessments must utilize the same CT/MRI/photographic method and acquisition technique (including use or non-use of IV contrast) as were used for screening assessments to ensure comparability. A chest x-ray or skeletal x-ray which clearly demonstrates a new metastatic lesion may be used to document progression in lieu of CT/MRI/bone scan.

Only those patients who have measurable disease present at baseline, have received at least 3 weeks of therapy, and have had their disease re-evaluated will be considered evaluable for response. These patients will have their response classified according to the definitions stated below.

#### **Measurability of tumour at baseline**

##### Measurable lesions

Lesions that can be accurately measured in at least one dimension with longest diameter  $\geq 10$  mm (by CT scan, MRI, caliper measurement) or  $\geq 20$  mm (by chest X-ray).

**Proprietary confidential information.**

© 2016 Boehringer Ingelheim International GmbH or one or more of its affiliated companies. All rights reserved.

This document may not - in full or in part - be passed on, reproduced, published or otherwise used without prior written permission.

Pathological lymph nodes, defined as lymph nodes with a short axis >15mm are also measurable.

#### Measurable disease

Measurable disease requires the presence of at least one measurable lesion.

#### Non-measurable disease

Non-measurable lesions are all other lesions, including small lesions (longest diameter <10 mm with CT scan, MRI or caliper measurement or <20 mm with chest X-ray or pathological lymph nodes with shortest axis  $\geq 10$  and <15 mm) as well as truly non-measurable lesions. Lesions considered truly unmeasurable include leptomeningeal disease, ascites, pleural or pericardial effusion, inflammatory breast disease, lymphangitic involvement of skin or lung, abdominal masses/ abdominal organomegaly identified by physical exam that is not measurable by reproducible imaging techniques.

#### New lesions in irradiated fields

Previously irradiated lesions should not be used as indicator lesions. However, new lesions occurring in previously irradiated fields can be used to assess the antitumour response.

### **Methods of measurement**

All measurements must be recorded in metric notation, using a ruler or calipers. All baseline evaluations must be performed as close as possible to the treatment start and never more than 4 weeks before the beginning of the treatment. If a lesion is considered too small to measure, a default measurement of 5mm should be applied. If the lesion is not visible, a default measurement of 0mm should be applied.

The same method of assessment and the same technique must be used to characterise each identified and reported lesion at baseline and during follow-up.

Clinical lesions will only be considered measurable when they are superficial (e.g., skin nodules, palpable lymph nodes). In the case of skin lesions, documentation by colour photography including a ruler to estimate the size of the lesion is obligatory.

CT and MRI are the best currently available and reproducible methods to measure target lesions selected for response assessment. Conventional CT and MRI should be performed with cuts of 5 mm or less in slice thickness contiguously. Spiral CT should be performed using a 5 mm contiguous reconstruction algorithm. This applies to the chest, abdomen and pelvis.

Ultrasound, endoscopy and laparoscopy should not be used to measure tumour lesions or evaluate tumour response. However, these techniques can be useful to supplement information from other techniques.

**Proprietary confidential information.**

© 2016 Boehringer Ingelheim International GmbH or one or more of its affiliated companies. All rights reserved.

This document may not - in full or in part - be passed on, reproduced, published or otherwise used without prior written permission.

Cytology and histology can be used to differentiate between PR and CR in rare cases (for example, residual lesions in tumour types such as germ cell tumours where known residual benign tumours can remain).

### Baseline Documentation of Target and Non-target Lesions

All measurable lesions up to a maximum of two lesions per organ and five lesions in total, representative of all involved organs should be identified as target lesions and will be recorded, measured (longest diameter = LD) and numbered at baseline. Target lesions should be selected on the basis of their size (lesions with the longest diameter) and their suitability for accurate repetitive measurements (either by imaging techniques or clinically). Lymph nodes must be  $\geq 15$ mm in order to be considered as target lesions.

A sum of the longest diameter (LD) for all target lesions will be calculated and reported as the baseline sum LD. The baseline sum LD will be used as reference to further characterise the objective tumour response of the measurable dimension of the disease (see Table 10.1: 1).

Table 10.1: 1 Evaluation of target lesions

Complete Response (CR)	Disappearance of all target lesions.
Partial Response (PR)	At least a 30% decrease in the sum of LD of target lesions taking as reference the baseline sum LD.
Progression (PD)	At least a 20% increase in the sum of LD of target lesions taking as reference the smallest sum LD recorded since the treatment started, together with an absolute increase in the sum of LD of at least 5mm. OR The appearance of one or more new lesions.
Stable Disease (SD)	Neither sufficient shrinkage to qualify for PR, taking as reference the baseline SoD, nor sufficient increase to qualify for PD taking as reference the smallest SoD since the treatment started.

All other lesions (or sites of disease) should be identified as non-target lesions and should also be recorded at baseline. Measurements are not required and these lesions should be followed as “present” or “absent” (see Table 10.1: 2).

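### Appendix 10.1 qualifies lymph nodes by short axis but sums them by longest diameter, so a site call of PD, SD or PR in nodal disease can depend on which axis is read

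*Protocol*

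**What the plan says.** Protocol Section 5.1.2.1 sends the reader to Appendix 10.1 for the detail of the RECIST 1.1 assessment. On nodes, the appendix says:

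- **Measurable lesions:** "Pathological lymph nodes, defined as lymph nodes with a short axis >15mm are also measurable".
- **Non-measurable disease:** the examples of small lesions include "or pathological lymph nodes with shortest axis" from 10 mm to below 15 mm.
- **Target selection:** targets come from the measurable lesions. Nodes must be at least 15 "mm in order to be considered as target lesions"; the axis is not named.
- **Measurement:** targets are "measured (longest diameter = LD) and numbered at baseline". The sum follows: "A sum of the longest diameter (LD) for all target lesions will be calculated and reported as the baseline sum LD". Neither statement makes an exception for nodes.
- **Table 10.1: 1:** CR is "Disappearance of all target lesions". PR is "At least a 30% decrease in the sum of LD of target lesions taking as reference the baseline sum LD". PD is a rise of at least 20% and at least 5 mm in the sum of LD from its smallest value, or a new lesion. SD refers to SoD, which is not defined.

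Primary PFS, the response tests and tumour shrinkage use central imaging (Protocol 7.3.1.1; SAP 7.4, 7.5.2.1, 7.5.2.2). Protocol 5.1.2.1.1 says that the central review will modify the conventional RECIST 1.1 measurement rules, but does not describe the modifications.

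**The concern.** A node enters on one axis and is followed on another, and a nodal target must vanish for CR although the appendix stops listing nodes as pathological below 10 mm. With two names for the reference sum and a target limit that names no axis, two careful readers could score the same scan differently.

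At stake are the calls made at the sites. Site assessment is enough to decide whether treatment continues (Protocol 3.1). Site PD or death supplies the 130 events among the first 176 patients for the interim analysis (Protocol 7.3.4). Site data also feed the investigator PFS dataset (SAP 7.4) and the investigator response summaries (SAP 7.5.2.1).

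**Working it through.** The plan gives no figure on this point to reproduce, and no sample size, power or alpha value depends on it. The check has two parts.

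**1. Does the axis change the category?**

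The thresholds are those of Table 10.1: 1:

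- PR if (baseline sum − current sum) / baseline sum is at least 30%.
- PD if (current sum − smallest sum) / smallest sum is at least 20% and the rise is at least 5 mm.

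Lesion sizes are assumed, in mm. Each case has one node and at most one other target lesion, read at baseline and at one follow-up, so baseline is also the smallest earlier sum.

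| Case | Other lesion | Node LD | Node short axis | Sum with node LD (as written) | Sum with node short axis |
|---|---|---|---|---|---|
| 1 | none | 25→31 | 16→16 | 25→31: 6/25 = +24.0%, +6 mm, **PD** | 16→16: 0%, **SD** |
| 2 | 30→22 | 32→26 | 20→12 | 62→48: −14/62 = −22.6%, **SD** | 50→34: −16/50 = −32.0%, **PR** |
| 3 | 20→20 | 32→36 | 18→26 | 52→56: 4/52 = +7.7%, **SD** | 38→46: 8/38 = +21.1%, +8 mm, **PD** |
| 4 | 20→20 | 25→35 | 18→20 | 45→55: 10/45 = +22.2%, +10 mm, **PD** | 38→40: 2/38 = +5.3%, **SD** |
| 5 | 30→21 | 30→21 | 20→14 | 60→42: −18/60 = −30.0%, **PR** | 50→35: −15/50 = −30.0%, **PR** |
| 6 | 34→0 | 26→18 | 16→9 | 60→18: −42/60 = −70.0%, **PR** | 50→9: −41/50 = −82.0%, PR unless a nodal CR rule applies |

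Cases 1 to 4 change category, and the direction varies. Case 5 shows the limit: if every target diameter changes by the same factor, both sums change by the same percentage. The 5 mm condition can still separate them when a sum is below 5/0.20 = 25 mm. For the node in case 1, a proportional 20% rise is 0.20 × 25 = 5 mm on LD but 0.20 × 16 = 3.2 mm on short axis.

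In case 6 the remaining node is outside the range that the appendix lists as pathological, yet CR is not met. Appendix 10.1 (Methods of measurement) gives 0 mm only to a lesion that cannot be seen.

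**2. Which analyses are reached?**

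- *Directly:* the site-based uses named above.
- *Indirectly, primary PFS.* Radiologically documented PD stops study drug (Protocol 3.3.4.1). Patients who stop for that reason are excepted from continued tumour assessment (Protocol 3.3.4.1.1). If the central reader has not called PD by then, the patient can be censored: under Rule 4 of Table 7.4: 1 if new anti-cancer medication starts first, or under Rule 7 if alive without central progression. A death before the next scheduled assessment is still an event (Rule 3a).
- *Not reached:* objective response counts CR and PR alike, and disease control counts CR, PR and SD (the SAP adds non-CR/non-PD). Reading CR as PR changes neither.

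**The case against.** The case on the other side is substantial, and much of it stands.

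- **Central review.** A reader might infer that the primary PFS result is mis-scored. The documents do not show this. The primary reads follow modified rules that are not described, so one cannot say that the LD sum governs them. Equally, one cannot say that they use short axis, or the same axis as the sites.
- **The 15 mm limits.** A reader might infer that a 15 mm node is unclassified. It is not: the non-measurable category takes in every lesion that is not measurable, and the 10 to below 15 mm range is an example within it. Targets are drawn from measurable lesions, so the mismatch touches at most a node recorded at exactly 15 mm.
- **The CR rule.** A reader might infer that it lowers the response or disease control rate. It does not, as shown above. Only the descriptive split between CR and PR moves.
- **Like with like.** Baseline and later sums both use LD, so change over time is measured consistently. Qualifying on one axis and following on another is not in itself a contradiction, and no passage says that short axis gives the true score. This stands against calling the LD result an error. It does not explain the unnamed axis in the target limit, the CR rule for small nodes, or SoD.
- **Size.** The examples use chosen geometry. The same rule applies in both arms, and no between-arm bias is shown.

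**Conclusion.** Appendix 10.1 is internally inconsistent on lymph nodes, and this can be seen without any outside source. Applied as written, it can give a different PD, SD or PR call from a short-axis reading, in either direction.

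The frequency cannot be estimated. The documents give neither the share of patients with nodal targets nor the shape of the nodes, and the table in the check rests on assumed sizes. The exposure that can be shown is site assessment, together with possible censoring in central PFS when a site PD ends imaging before central progression. The documents do not support the stronger conclusion that the centrally read endpoints are wrong.

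**What to change.** In Appendix 10.1, reconcile the sections on measurable lesions, non-measurable disease and target lesions:

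1. Enter nodal targets into the sum by the short axis that already qualifies them.
2. State a CR rule for nodal targets that agrees with the 10 mm lower bound in the non-measurable section.
3. Use one 15 mm limit for nodes throughout, with the axis named.
4. Use one term, *sum of diameters*, in all rows of Table 10.1: 1, in line with the SAP's tumour shrinkage section.
5. State that site and central reads use the same axis, or say how the modifications in Protocol 5.1.2.1.1 differ.

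The Amendment 2 description in Protocol Section 11 says that PFS has already been assessed and reported. For that analysis, document which nodal axis the central readers and the sites used. The corrected wording then serves the remaining site reads, which are the only reads once central review ends under Protocol Version 3.0.

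The cost is appendix wording and a memo to sites. No new scans are needed, because both axes can be read from existing images.

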**Proprietary confidential information.**

© 2016 Boehringer Ingelheim International GmbH or one or more of its affiliated companies. All rights reserved.

This document may not - in full or in part - be passed on, reproduced, published or otherwise used without prior written permission.

Table 10.1: 2 Evaluation of non-target lesions and new lesions

Complete Response (CR)	Disappearance of all non-target lesions and normalisation of tumour marker level.
Non-CR/ Non-PD	Persistence of one or more non-target lesions or/and maintenance of tumour marker level above normal limits.
Progression (PD)	Appearance of one or more new lesions and/or unequivocal progression of existing non-target lesions.  Although a clear progression of non-target lesions only is exceptional, in such circumstances, the opinion of the treating physician should prevail and the progression status should be confirmed later by the review panel (or study chair).

In some circumstances it may be difficult to distinguish residual disease from normal tissue. When the evaluation of complete response depends upon this determination, it is recommended that the residual lesion be investigated (fine needle aspirate/biopsy) before confirming the complete response status.

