### Evaluation of Best Response to Study Treatment

The best response to study treatment (Table 10.1: 3) is the best response recorded from the start of treatment until disease progression or start of further anti-cancer treatment (taking as reference for progressive disease the smallest measurements recorded since the treatment started). In general, the patient's best response assignment will depend on the achievement of both measurements and confirmation criteria (Table 10.1: 3).

Patients with a global deterioration of health status requiring discontinuation of treatment without objective evidence of disease progression at that time should be reported as "*symptomatic deterioration*". Every effort should be made to document the objective progression even after discontinuation of treatment.

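### Appendix 10.1 judges target-lesion progression against the smallest on-treatment sum, which read literally leaves out the pre-treatment baseline and conflicts with the sentence above the table

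*Protocol*

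**What the plan says.** All of the wording at issue is in protocol Appendix 10.1.

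- **PD row, Table 10.1: 1.** Target-lesion PD is an increase of at least 20% in the sum of longest diameters, "taking as reference the smallest sum LD recorded since the treatment started". The sum must also have risen by 5 mm or more. Separately, "The appearance of one or more new lesions" is enough.
- **SD row, same table.** Shrinkage is judged against the baseline sum, but growth is judged differently: "nor sufficient increase to qualify for PD taking as reference the smallest SoD since the treatment started".
- **Best-response paragraph.** It repeats the reference: "taking as reference for progressive disease the smallest measurements recorded since the treatment started".
- **Sentence above the table.** "The baseline sum LD will be used as reference to further characterise the objective tumour response of the measurable dimension of the disease", with a pointer to Table 10.1: 1.
- **Timing of baseline.** The Methods of measurement paragraph puts baseline evaluations before treatment, "never more than 4 weeks before the beginning of the treatment". The flow chart (footnote 12) and Section 6.2.1 allow the screening scan up to 21 days before randomisation. SAP Section 6.7 takes baseline as the last value before the first dose.
- **Non-target disease, Table 10.1: 2.** PD is "Appearance of one or more new lesions and/or unequivocal progression of existing non-target lesions", with no reference sum involved.

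Scans follow at weeks 8, 12 and 16 and every 8 weeks after that. German sites may use an X-ray instead of CT or MRI at week 12.

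**The concern.** A baseline sum measured before the first dose was not recorded after treatment began. If the three phrases are taken at their word, the week-8 scan has no earlier sum to be compared with. A target-lesion sum that is 50% above baseline at week 8, with no new lesion and no non-target progression, is then not PD and falls into the SD row. A week-8 scan also meets the six-week minimum for SD in the Confirmation paragraph, so that patient could count as having disease control. From then on the tumour is judged against its already enlarged week-8 size.

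The two readings differ only while the baseline sum is smaller than every on-treatment sum. For a tumour that first shrinks below baseline they agree.

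Several results rest on this definition. Section 5.1.2.1 sends the reader to Appendix 10.1 for the details of RECIST assessment, so it bears on PFS. It bears on the site-assessed count of 130 events for the interim analysis (Section 7.3.4) and on the investigator-assessed PFS data (SAP Section 7.4). It also bears on discontinuation for radiological progression (Section 3.3.4.1). If readers resolve the wording differently, the same scans give different progression dates.

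**Working it through.** **1. The plan's own figure.** No passage states a delay. The nearest design figure is 372 PFS events for 90% power at a hazard ratio of 0.714, two-sided alpha 0.05, 1:1 (Section 7.6). Schoenfeld's formula is 4(z₀.₉₇₅ + z₀.₉₀)² / (ln HR)². With HR = 10/14 it gives 4(1.960 + 1.282)² / 0.1132 ≈ 372; with HR = 0.714 rounded it gives 371. The event target reproduces and is not in dispute.

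**2. Set-up for the delay.** From the documents: scans at weeks 8, 12, 16, 24, 32, 40; the 20% and 5 mm rule; a baseline scan up to 3 weeks before randomisation. Assumed, because the documents give no growth data: steady exponential or linear growth; T = 2 to 24 weeks from the baseline scan to reach +20%; baseline sums of 30, 60 or 100 mm. The baseline scan is b = 0 or 3 weeks before randomisation. The 5 mm condition binds only when the reference is below 5/0.20 = 25 mm, so the three baseline sums give identical results.

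**3. Formulas** (t = weeks from randomisation):
- Baseline counted, either growth shape: PD at the first scan with t ≥ T − b.
- As written, exponential: the reference is the week-8 sum, so PD is at the first later scan with t ≥ T + 8.
- As written, linear: 1 + 0.2(t + b)/T ≥ 1.2[1 + 0.2(8 + b)/T], which gives t ≥ T + 9.6 + 0.2b.

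The two thresholds are at least 8 weeks apart and no scan interval exceeds 8 weeks. If PD would be called after week 8, the literal reading therefore moves it by at least one scan. If it would be called at week 8, the literal reading cannot call it before week 12.

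**4. One case in full.** Baseline 80 mm, exponential, T = 8, b = 0. The sums are 96.0 mm (week 8), 105.2 mm (week 12) and 115.2 mm (week 16). With baseline counted, 96.0/80 = 1.20 and +16 mm, so PD at week 8. As written, week 12 gives 105.2/96.0 = 1.10 (not PD) and week 16 gives 115.2/96.0 = 1.20 and +19.2 mm, so PD at week 16.

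**5. Exponential growth, b = 0:**

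| T, weeks to +20% | PD, baseline counted | PD, as written | Delay |
|---|---|---|---|
| 2 to 4 | week 8 | week 12 | 4 weeks |
| over 4 to 8 | week 8 | week 16 | 8 weeks |
| over 8 to 12 | week 12 | week 24 | 12 weeks |
| over 12 to 16 | week 16 | week 24 | 8 weeks |
| over 16 to 24 | week 24 | week 32 | 8 weeks |

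**6. Other assumptions:**

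| Growth | Baseline scan | Delays found |
|---|---|---|
| Exponential | 3 weeks before | 4, 8, 12 or 16 weeks |
| Linear | week 0 | 4, 8, 12 or 16 weeks |
| Linear | 3 weeks before | 8, 12, 16 or 20 weeks |
| Either, no week-12 CT/MRI (German sites) | either | 8 or 16 weeks |

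The 20-week case, for example: linear, b = 3, T = 14. With baseline counted, t ≥ 11, so week 12. As written, t ≥ 14 + 9.6 + 0.6 = 24.2, so week 32.

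**7. How much could fall at the first scan.** If PFS were exponential with the planned medians, 1 − 2^(−8/10) = 43% of erlotinib patients and 1 − 2^(−8/14) = 33% of afatinib patients would have an event by week 8. These are events of every kind. The share due to target growth alone is not given.

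**The case against.** The strongest reply is that no sensible reader would apply the literal text. The sentence just above the table names the baseline sum as a reference for it, and the Methods paragraph wants baseline close to treatment start. The literal reading also leaves the PD test without a reference at the first scan. Primary PFS invokes RECIST 1.1 as cited and rests on blinded central imaging (Section 7.3.1.1), and Appendix 10.1 describes itself only as based on that guideline.

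Part of this stands. The text is in conflict with itself, and nothing shows that anyone chose to exclude baseline. But the baseline sentence is general and hands the reader to a table that names baseline for response and a different reference for progression; the SD row sets the two side by side. Central review does not settle it: Section 5.1.2.1.1 announces modified measurement criteria and refers to specifications in the investigator site file, which is not among the documents.

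Two stronger readings are tempting. A reader might infer that progression is called 8 to 12 weeks late. That range fits exponential growth reaching +20% in more than 4 weeks with baseline at randomisation; other equally unverified assumptions give 4, 16 or 20 weeks. A reader might also infer that the primary PFS result is delayed or biased. The documents do not show which reference was used, the rule is the same in both arms, and the share of events due to target growth alone is not stated.

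**Conclusion.** The point holds as a conflict in the wording of the progression definition, worth correcting. Taken literally, the PD row, the SD row and the best-response paragraph exclude the pre-treatment baseline sum. Target growth alone then cannot be PD at week 8, and a steadily growing tumour is called PD at least one scan interval late. The range of 4 to 20 weeks rests on the assumed growth shapes, T from 2 to 24 weeks, and a baseline scan 0 to 3 weeks before randomisation. It can be set against planned medians of 10 and 14 weeks, but it is not an estimate of any shift in those medians.

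New lesions, non-target progression and death are unaffected, and the 372-event calculation stands. A delay shared by every patient would leave the log-rank ordering unchanged. Here only some events could move, so the ordering could change, but the effect on the hazard ratio cannot be sized from the documents.

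**What to change.** Reconcile three phrases in Appendix 10.1 (the PD and SD rows of Table 10.1: 1 and the best-response paragraph) with the baseline sentence above the table. For the PD endpoint, say expressly that the smallest sum includes the baseline sum.

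Also state, in the SAP or the trial report, which reference the central readers applied for PFS and which the sites applied for investigator-assessed PFS and for the interim count. Central review ends under protocol Version 3.0 (Sections 3.1 and 5.1.2.1.1), so for the primary analysis this statement matters more than any change to reading instructions. If some readers left baseline out, the recorded target-lesion sums should allow a sensitivity analysis.

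The same text feeds the decision to stop study drug. For that use the point is only that the passages must be reconciled; no treatment rule is proposed.

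The cost is three phrases and one clarifying statement, with no new scans or patients.
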